**11 APPENDICES**

## Appendix A: Derived Variables

The table below provides the list of derived variables for demographic and baseline characteristics, various duration derivations, drug compliance, baseline derivations and other important derivations applicable for this study.

Variables	Formula
Demographic and Baseline characteristics	
Age (in years)	For patients not from France and Germany, age will be calculated based on date of birth. For patients from France and Germany, only birth year was collected, and July 1 was imputed in the eDC system. The CRF collected age months and age years are based on the imputed date of birth. For analysis purpose, age will be calculated based on collected age months and age years on CRF or the external file (primary source).
Body mass index (BMI) (kg/ m  )	weight (kg)/[height (m  )
PFIC diagnosis (in years)	Will be derived by SAS YRDIF function yrdif (date of diagnosis of PFIC, Date of informed consent, 'ACT/ACT');
Derivation of Duration	
Study day at any visit	Date of interest – date of first dose of study drug. One day is added if this difference is $\geq 0$
Extent of Exposure (days)	Date of last study drug intake – Date of first study drug intake + 1
Overall Study Drug Compliance	
Compliance based on CRF data	$100 \times [(total\ number\ of\ capsules\ dispensed - total\ number\ of\ capsules\ returned) / (total\ number\ of\ capsules\ planned\ to\ be\ taken)]$
Compliance based on eDiary data	100 x (total number of capsules taken/total number of capsules planned to be taken). This will be considered as the primary compliance rate.  The number of capsules planned to be taken will be estimated based on patient's body weight at Visit 3 and Visit 6 per Table 2 in the protocol. The number of capsules planned to be taken before Visit 6 will be the same as the one estimated at Visit 3, and after Visit 6 will be the same as the one estimated at Visit 6.
Derivations for Efficacy Parameters	
Baseline (general)	The baseline value of a parameter is defined as the last assessment of that parameter prior to the first intake of study treatment, except as indicated below.


Baseline for proportion of patients experiencing at least a 70% reduction in fasting s-BA and for s-BA change from baseline
	
Fasting s-BA baseline will be calculated as the average of the last 2 values prior to the first dose (see also Appendix B). If only one non-missing value is available, it will be used as baseline.

End value for proportion of patients experiencing at least a 70% reduction in fasting s-BA and for s-BA change from baseline
	
The end value is the average of the values at Weeks 22 and 24 after the start of double-blind treatment. (Appendix B). If one value is missing, then the non-missing value will be used as the end value. If both values are missing, then the end value is missing.

Baseline, daily, weekly and monthly score by AM and PM respectively (scratching, itch severity)
	
For both the Albireo ObsRO scratching item and the Albireo PRO itch severity score:
 
All non-missing AM scores from the period of 14 days prior to or on the first dose day of study medications will be averaged as baseline.
 
All non-missing PM scores from the period of 14 days prior to the first dose day of study medications will be averaged as baseline.
 
Baseline score will be considered missing if <math>\geq 8</math> out of 14 assessments in the 14 days are missing (i.e. 50% rule is applied based on the number of planned assessments).
 
A weekly AM (PM) score will be calculated by averaging all non-missing AM (PM) scores in a week. A weekly score will be considered missing if <math>\geq 4</math> out of 7 AM (PM) scores in a week are missing.
 
A bi-weekly AM (PM) score will be calculated by averaging all non-missing AM (PM) scores in 2 weeks. A bi-weekly score will be considered missing if <math>\geq 8</math> out of 14 AM (PM) scores in 2 weeks are missing.
 
A monthly AM (PM) score will be calculated by averaging all non-missing AM (PM) scores in a month (28 days). A monthly score will be considered missing if <math>\geq 15</math> out of 28 AM (PM) scores a week are missing.


AM & PM baseline, daily, weekly and monthly score (scratching, itch severity)
	
For both the Albireo ObsRO scratching item and the Albireo PRO itch severity score:
 
A daily AM & PM score will be averaged from the 2 ratings for each day. A daily score will be considered missing if both assessments are missing.
 
A weekly score will be calculated by averaging all non-missing AM and PM scores in a week. A weekly score will be considered missing if <math>\geq 8</math> out of 14 assessments in a week are missing.
 
A bi-weekly score will be calculated by averaging all non-missing AM and PM scores in 2 weeks. A bi-weekly score will be considered missing if <math>\geq 15</math> out of 28 assessments in 2 weeks are missing.
 
A monthly score will be calculated by averaging all non-missing AM and PM scores in a month (28 days). A monthly score will be considered missing if <math>\geq 29</math> out of 56 assessments in a month are missing.

	
All non-missing AM scores from the period of 14 days prior to or on the first dose day of study medications, and all non-missing PM scores from the period of 14 days prior to the first dose day of study medications will be averaged as the AM & PM baseline score. Baseline score will be considered missing if <math>\geq 15</math> out of 28 assessments in the 14 days are missing. One thing of note:
 
Inclusion criteria #4: Patient must have history of significant pruritus and a caregiver-reported observed scratching in the eDiary average of <math>\geq 2</math> (on 0 to 4 scale) in the 2 weeks prior to randomization.
 
The pruritus score for purposes of establishing eligibility was calculated by taking the average of the worse of the two scores for each day. The values for week one were averaged and the values for week 2 were averaged. The two weekly averages were then averaged to provide a single score. If this score was <math>\geq 2</math> the pruritus eligibility requirement was met. The calculation of pruritus eligibility score is different from the calculation of the baseline pruritus score defined in the SAP.


Average of change from baseline from each AM and PM score (scratching, itch severity)
	
The calculation below is based on the change from baseline in each AM and PM score. The values based on this calculation will be used for data analysis.
 
Change from baseline (daily) will be calculated by averaging all non-missing values of change from baseline (AM and PM) in a day. A daily change from baseline will be considered missing if both AM and PM change from baseline in a day are missing.
 
Change from baseline (weekly) will be calculated by averaging all non-missing values of change from baseline (AM and PM) in a week. A weekly change from baseline will be considered missing if <math>\geq 8</math> out of 14 change from baseline values in a week are missing.
 
Change from baseline (bi-weekly) will be calculated by averaging all non-missing values of change from baseline (AM and PM) in a week. A weekly change from baseline will be considered missing if <math>\geq 15</math> out of 28 change from baseline values in a week are missing.
 
Change from baseline (monthly) will be calculated by averaging all non-missing values of change from baseline (AM and PM) in a month (28 days). A monthly change from baseline will be considered missing if <math>\geq 29</math> out of 56 assessments in a month are missing.

Baseline, daily, weekly and monthly (sleep parameters, such as difficulty of falling asleep and staying asleep, tiredness, the number of awakenings)
	
For patient- and observer reported outcome scores of sleep parameters, the same approach above will be used as for scratching/itch severity by AM and PM respectively since there is just 1 rating per day.

Proportion of positive pruritus assessments
	
In the primary analysis of the pruritus endpoint, all intermittently missing assessments will be classified as negative pruritus assessments. Similarly, all missing planned assessments after discontinuation of study drug will be counted as negative pruritus assessments. All planned assessments after death or initiation of rescue treatments such as biliary diversion surgery or liver transplantation will be counted as negative pruritus assessments. Both on-treatment and off-treatment pruritus assessments up to Day 168 will be included for analysis.

	
Rounded baseline score will be used for the primary analysis. Additional analysis will be conducted based on unrounded baseline score.
 
In general, all 336 assessments planned over the 24-week treatment period will be included in the denominator of the endpoint definition. However, if a completer's last pruritus assessment is reported prior to Day 168, then (the last report day x 2) will be used as the denominator. The last report day will be determined for ObsRO and PRO instruments separately.
 
Regarding the proportion of positive pruritus assessments for each 4-week interval, the proportion is calculated up to the last interval with at least 50% of planned assessments.

Derivations for Safety Parameters	
Adverse Events (AE) duration (days)	AE end date – AE start date +1
Treatment Emergent Adverse Event (TEAE)	An AE (classified by preferred term) that occurs during the Treatment Period will be considered a TEAE if it has a start date on or after the first dose date of study drug, or it has a start date before the date of the first dose date of study drug, but worsened in severity on or after the date of the first dose date of study drug.

## Appendix B: Visit Window

The observation closest to the target day is the measurement used in the analysis for each visit. The following 3 tables of analysis visit windows will apply for laboratory parameters, questionnaires, vital signs, physical measurements and other efficacy parameters in the study, if not otherwise specified.

Table 3.1: Analysis Visit Windows (General)

Timing of assessment (days relative to Treatment)	Visit Name to display for Analysis	Target day	Study Day (Relative Day)
Screening (Days -56 to -1)	Baseline		<= -1
Day 1 Week 1	Baseline		1 (pre-dose)
Week 4 ( $\pm$ 3 days)	Week 4	28	Post-baseline - 42
Week 8 ( $\pm$ 3 days)	Week 8	56	43 - 70
Week 12 ( $\pm$ 3 days)	Week 12	84	71 - 105
Week 18 ( $\pm$ 3 days)	Week 18	126	106 - 140
Week 22 ( $\pm$ 3 days)	Week 22	154	141 - 161
Week 24/EOT ( $\pm$ 3 days)	Week 24	168	162 - (last dose day + 14)
4 Weeks Post Last Dose of Study Drug ( $\pm$ 3 days)	Follow-up	28 post last dose	$\geq$ Last dose day + 15

Table 3.2: Analysis Visit Windows for GIC/GIS, Physical Measurements and Selected Lab Tests

Timing of assessment (days relative to Treatment)	Visit Name to display for Analysis	Target day	Study Day (Relative Day)
Screening (Days -56 to -1)	Baseline		<= -1
Day 1 Week 1	Baseline		1 (pre-dose)
Week 4 ( $\pm$ 3 days)	Week 4	28	Post-baseline - 56
Week 12 ( $\pm$ 3 days)	Week 12	84	57 - 126
Week 24/EOT ( $\pm$ 3 days)	Week 24	168	127 - (last dose day + 14)
4 Weeks Post Last Dose of Study Drug ( $\pm$ 3 days)	Follow-up	28 post last dose	$\geq$ Last dose day + 15

Note: Physical measurements include physical examination, voluntary photography and skin examination. Selected lab tests include urinalysis, autotaxin, p-C4, Vitamins A & E and 25-hydroxy vitamin D.

Table 3.3: Analysis Visit Windows for PedsQL, Fibroscan, Abdominal Ultrasound and AFP

Timing of assessment (days relative to Treatment)	Visit Name to display for Analysis	Target day	Study Day (Relative Day)
Screening (Days -56 to -1)	Baseline		<= -1
Day 1 Week 1	Baseline		1 (pre-dose)
Week 24/EOT ( $\pm$ 3 days)	Week 24	168	71 - (last dose day + 14)
4 Weeks Post Last Dose of Study Drug ( $\pm$ 3 days)	Follow-up	28 post last dose	$\geq$ Last dose day + 15

For laboratory and non-laboratory parameters, if a patient has more than one measurement included within a window, the assessment closest to the target day will be used. In case of ties between observations located on different sides of the target day, the earlier assessment will be used. For laboratory parameters, central laboratory results will be used over local laboratory results if both are in a same analysis window.

Derivations for pruritus and other itching, scratching, sleep parameters measured by the Albireo ObsRO and PRO instruments will be derived based on the following analysis window. For analysis purposes, diary entries will be assigned to a study day based on the recorded date regardless of recorded time. Please also refer to the derivations in the table of derived variables in [Appendix A](#) for details.

Analysis Window	Treatment Period	Start Study Day	End Study Day
Baseline	Week 0 (randomization)+	Day -14, PM assessment	Day 1, AM assessment
Week 4	Week 4	Day 1, PM assessment	Day 29, AM assessment
Week 8	Week 8	Day 29, PM assessment	Day 57, AM assessment
Week 12	Week 12	Day 57, PM assessment	Day 85, AM assessment
Week 16	Week 16	Day 85, PM assessment	Day 113, AM assessment
Week 20	Week 20	Day 113, PM assessment	Day 141, AM assessment
Week 24	Week 24 (EOT)	Day 141, PM assessment	Day 169, AM assessment
Follow-up	Week 28 (Follow-up)	Date of EOT PM assessment	Date of EOT + 28 days AM assessment

## Appendix C: Definition of Region Variable

Country	Country code	Region variable
Australia	AUS	RoW
Belgium	BEL	EU
Canada	CAN	RoW
France	FRA	EU
Germany	DEU	EU
Israel	ISR	RoW
Italy	ITA	EU
Netherlands	NLD	EU
Poland	POL	EU
Saudi Arabia	SAU	RoW
Spain	ESP	EU
Sweden	SWE	EU
Turkey	TUR	RoW
United Kingdom	GBR	EU
United States	USA	US

## Appendix D: Handling of Missing or Incomplete Dates

Global statement:

If the imputed date is prior to the date of birth, then impute the missing date as date of birth.

Imputation rules for missing or partial AE start date are defined below:

### **If only Day of AE start date is missing:**

If the AE start year and month are the same as that for the first dose date, then:

- If the full (or partial) AE end date is NOT before the first dose date or AE end date is missing, then impute the AE start day as the day of first dose date;
- If AE end date is prior to first dose date, then impute the AE start day as 1.

### **If Day and Month of AE start date are missing:**

If AE start year = first dose year, then:

- If the full (or partial) AE end date is NOT before the first dose date or AE end date is missing, then impute the AE start month and day as the month and day of first dose date;
- If AE end date is prior to first dose date, then impute the AE start month as January and the day as 1.

### **If Year of AE start date is missing:**

If the year of AE start is missing or AE start date is completely missing, then query the site with no imputation. Also compare the full (or partial) AE end date to the first dose date. If the AE end date is before the first dose date, then the AE should be considered as a pre-treatment AE.

Otherwise, the AE will be considered as TEAE.

Imputation rules for missing or partial non-study medication start/stop dates are defined below:

### **Missing or partial non-study medication start date:**

- If only day is missing, use the first day of the month.
- If day and month are both missing, use the first day of the year.
- If day, month and year are all missing, use the date of the day before the first dose date.

### **Missing or partial non-study medication stop date:**

- If only day is missing, use the last day of the month.
- If day and month are both missing, use the last day of the year.
- If day, month and year are all missing, assign 'continuing' status to stop date

## Appendix E: SAS Codes

### 1. Cochran-Mantel-Haenszel test

```
Proc freq data=<>;  
  tables pfic*ageclass*trt*responder/cmh commonriskdiff;  
  exact comor;  
  ods output cmh=cmh (where=(AltHypothesis="General Association"));  
run;
```

### 2. ANCOVA model

```
Proc mixed data=<>;  
  class trt(ref='Placebo') pfic ageclass;  
  model proportion of positive assessment = trt baseline pfic ageclass / solution;  
  lsmeans trt / cl diff alpha=0.05;  
  lsmestimate trt 'total odevixibat dose' 0.5 0.5 0 ;  
  lsmestimate trt 'avg odevixibat dose effect - placebo' 0.5 0.5 -1/ cl alpha=0.05;  
run;
```

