## 5 SAMPLE SIZE AND POWER

For the EU and RoW, the primary analysis will be related to the serum bile acid responder endpoint. For the US, the primary analysis will be related to the pruritus endpoint. The CMH test stratified by randomization strata will be used to test the serum bile acid responder endpoint. The individual null hypothesis is that the odds ratio of the response in an active arm vs. placebo is 1. The alternative hypothesis is that the odds ratio is greater than 1. An ANCOVA will be used for treatment comparisons for the proportion of positive pruritus assessments at subject level. The individual null hypothesis is that the average proportion of positive assessments is the same between the active and placebo arms. The alternative hypothesis is that the average proportion is larger in the active arm.

Since each active arm will be compared with the placebo, there will be two individual null hypotheses for each endpoint. In each endpoint, a pooled analysis for the closed testing procedure will be applied to control the 1-sided overall type I error rate for the two odevixibat treatment comparisons vs. placebo at the 0.025 level [6,7,8]. The significance of an active arm will be claimed if both 1-sided p-values in the pooled analysis and individual treatment comparison are less than or equal to 0.025.

The study will enroll 60 to 70 patients in order to obtain at least 20 evaluable patients in each arm. For each primary endpoint, simulations with 5,000 iterations using 20 patients per arm were conducted to estimate the power after multiplicity adjustment, resulting in a standard error (SE) of <0.7% for each estimated power.

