### 8.6.1.3 Multiplicity

For EU and RoW, the primary analysis will be related to the serum bile acid responder endpoint. For US, the primary analysis will be related to the pruritus endpoint. For each primary endpoint, a pooled analysis for the closed testing procedure will be applied to control the 1-sided overall type I error rate for two treatment comparisons vs. the placebo at the 0.025 level as specified below:

In the closed testing procedure, the low and high dose groups are pooled to compare with the placebo group first. If the 1-sided p-value is  $\leq 0.025$ , the 1-sided p-values for low dose vs. placebo and high dose vs. placebo, respectively will be calculated. If both individual p-values are  $\leq 0.025$ , a significant treatment effect will be declared on both dose groups. If only one of them is  $\leq 0.025$ , a significant treatment effect will be declared on the corresponding dose group.

In testing the primary endpoint for US, treatment arms will be separated in the pooled analysis and the "lsmestimate" statement in SAS Proc Mixed will be used to compare pooled active arms vs. the placebo. See [Appendix E](#).

Adjusted p-values will also be reported when unadjusted p-values are presented directly from the model. The adjusted p-value for an individual dose is calculated as the maximum value of the unadjusted p-value for the pooled low and high doses and the unadjusted p-value for the individual doses.

Analyses of secondary and exploratory endpoints will provide supportive efficacy and safety information regarding the differences between the treatment groups. No adjustments will be performed for multiple comparisons when testing these secondary and exploratory endpoints.

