### 8.6.3 Analyses of primary efficacy endpoints

The primary analyses on the primary endpoints will be based on the FAS. Additional analyses on the primary endpoints will be conducted for PP analysis set.

For EU and RoW, proportion of patients experiencing at least a 70% reduction in fasting s-BA concentration from baseline to the end of treatment or reaching a level  $\leq 70$   $\mu\text{mol/L}$  after 24 weeks of treatment will be analyzed using the CMH test. Patients with missing data at the end of treatment will be classified as non-responders. CMH stratified by PFIC type and age category will be performed to compare the proportion of the responders in fasting bile acid at the end of treatment (based on average of Weeks 22 and 24). The testing procedure is addressed in the Section 8.6.1.3. The contrasts of primary interest will be the treatment differences at end of treatment (Week 22 and 24); also, the difference at Week 4, Week 8, Week 12, and Week 18 will

be estimated and analyzed.

For US, the primary endpoint is the proportion of positive pruritus assessments at the subject level over the 24-week Treatment Period. A positive pruritus assessment is defined as a scratching score of  $\leq 1$  or at least a one-point drop from baseline on the Albireo ObsRO instrument. At each assessment, the AM score will be compared to the baseline AM average, and the PM score will be compared to the baseline PM average. Both AM and PM pruritus assessments will be included in the analysis of this endpoint. For analysis purposes, diary entries will be assigned to a study day based on the recorded date regardless of recorded time. AM scores from the period of 14 days prior to or on the first dose day of study medication will be averaged as AM baseline. PM scores from the period of 14 days prior to the first dose day of study medication will be averaged as PM baseline. Baseline score will be rounded to an integer to evaluate the positive pruritus assessments for the primary analysis. Additional analysis will be conducted using unrounded baseline score.

An ANCOVA model will be used for treatment comparisons. The model will include treatment arm, AM baseline pruritus score, PM baseline pruritus score, and stratification factors, i.e., PFIC type and age category. The testing procedure is addressed in the section [8.6.1.3](#).

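### The Appendix E code does not match the primary analyses in the text: one undefined baseline term instead of two, and no step from its two-sided or 2-df output to the 1-sided p-values that the decision rule uses

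*SAP*

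**What the plan says.** **US primary model.** Section 8.6.3 of the SAP states: "The model will include treatment arm, AM baseline pruritus score, PM baseline pruritus score, and stratification factors, i.e., PFIC type and age category". It then sends the reader to Appendix E for the code. Section 8.6.1.3 does the same for the pooled contrast, saying that the `lsmestimate` "statement in SAS Proc Mixed will be used to compare pooled active arms vs. the placebo". The Appendix E model line is "model proportion of positive assessment = trt baseline pfic ageclass / solution".

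**Decision rule.** Section 5 claims significance for a dose when "both 1-sided p-values in the pooled analysis and individual treatment comparison are less than or equal to 0.025". The alternatives are directional; for s-BA, "The alternative hypothesis is that the odds ratio is greater than 1". Sections 8.1 and 8.6.1.3 repeat the 1-sided 0.025 level. Section 8.6.1.3 defines the adjusted p-value for a dose as the larger of the pooled and the individual p-value.

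**Code output.** The ANCOVA block uses `lsmeans` with differences and two `lsmestimate` lines, none with a one-sided option. The CMH block is "tables pfic*ageclass*trt*responder/cmh commonriskdiff" and keeps only the General Association row of the output.

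**The concern.** Appendix E is the only place where the SAP shows how the two primary tests are to be run, and it departs from the text in two ways.

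1. **Covariates.** Appendix A defines an AM baseline, a PM baseline and a combined AM and PM baseline. A programmer working from the model line could enter any of these as the single covariate. None gives the model of section 8.6.3. With about 20 patients per arm, the choice of covariates can move a p-value, so a primary model should not leave it open.

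2. **Sidedness and comparison.** The rule needs three 1-sided p-values per endpoint: pooled, low dose and high dose, each against placebo. The code yields two-sided p-values for the ANCOVA. For s-BA it yields a statistic with no direction which, with a three-level treatment variable, is none of the three comparisons. Section 8.6.1.3 also describes unadjusted p-values as coming straight from the model and gives no conversion. A literal user could therefore hold the wrong p-value against 0.025.

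**Working it through.** **1. The two ANCOVA models side by side**

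| Term | Section 8.6.3 | Appendix E |
|---|---|---|
| Treatment (3 arms) | yes | yes |
| AM baseline | yes | one term, not defined |
| PM baseline | yes | (same single term) |
| PFIC type, age category | yes | yes |

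With 60 patients and every level present, the residual df are 60 − (1 + 2 + 2 + 1 + 2) = 52 for the text and 60 − (1 + 2 + 1 + 1 + 2) = 53 for the code. The lost degree of freedom hardly matters. Any difference would come from how much outcome variance each baseline explains. That needs the AM/PM correlation and the correlations with the outcome. The SAP gives neither, so no size can be attached.

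**2. The plan's own power at 1-sided 0.025**

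Inputs from section 5: 20 per arm, pooled test first and then each dose, s-BA response 60% v 10% or 50% v 10%, pruritus effect size 1.0526. The s-BA check simulated binomial counts and an unstratified CMH statistic without continuity correction (200,000 runs). The pruritus check used beta-binomial data with 336 assessments per patient, SD = difference / 1.0526 and ANOVA contrasts on 57 df (40,000 runs, five scenarios).

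| Endpoint | Stated: one dose / at least one / both | Recomputed |
|---|---|---|
| s-BA 60% v 10% | 94 / 99 / 91% | 94.9 / 98.3 / 91.5% |
| s-BA 50% v 10% | 82 / 91 / 73% | 82.1 / 90.8 / 73.6% |
| Pruritus | 89 / 95 / 83% | 87.7–89.1 / 93.7–95.1 / 81.8–83.5% |

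All are within 2 points, so the stated power does rest on 1-sided 0.025.

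**3. What the CMH code keeps**

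Take one stratum, with 10/20 responders on each dose and 2/20 on placebo.

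- *One dose v placebo.* Expected count 20 × 12/40 = 6. Variance 20 × 20 × 12 × 28 / (40² × 39) = 2.154. Statistic (10 − 6)² / 2.154 = 7.43 on 1 df. Two-sided p = 0.0064; 1-sided p = 0.0032.
- *Direction reversed (2/20 v 10/20).* The statistic and the two-sided p = 0.0064 are the same, but the 1-sided p is 1 − 0.0064/2 = 0.997. The retained p-value cannot tell the two apart.
- *Pooled v placebo (20/40 v 2/20).* Expected count 40 × 22/60 = 14.67. Variance 40 × 20 × 22 × 38 / (60² × 59) = 3.149. Statistic (20 − 14.67)² / 3.149 = 9.03 on 1 df. Two-sided p = 0.0027; 1-sided p = 0.0013.
- *Code as written, three arms.* The statistic is again 9.03, because the two doses are equal here, but it is referred to 2 df: p = 0.0109.

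**4. Power if printed two-sided p-values were held to 0.025**

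For an effect favouring odevixibat, 1-sided p = two-sided p / 2. Requiring two-sided p ≤ 0.025 therefore means 1-sided p ≤ 0.0125, and the normal critical value rises from 1.960 to 2.241. Under the same simulations, with each two-group comparison run separately:

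| Endpoint | One dose / at least one / both |
|---|---|
| s-BA 60% v 10% | 90.2 / 96.2 / 84.3% |
| s-BA 50% v 10% | 72.1 / 83.8 / 60.2% |
| Pruritus, beta-binomial | 81.4–82.6 / 89.5–91.0 / 73.5–74.7% |

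A normal model for pruritus gives 83 to 84% for one dose, against 90% at 1-sided 0.025.

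**The case against.** Appendix E is a template. The data set is blank and the response is a phrase, not a valid variable name, so the single baseline may be shorthand. Section 8.6.4 reuses the primary model for AM-only and PM-only proportions, where one generic slot could fit. Section 8.6.3 is explicit and in the main text. The 1-sided rule appears in sections 5, 8.1 and 8.6.1.3, and section 8.6.1.3 sets out the pooled and individual comparisons in order. Halving a two-sided p-value is routine. The two-sided limits in the code are needed for the 95% confidence intervals of sections 8.1 and 8.6.3. The 0.5, 0.5, −1 contrast is right with placebo as the last level.

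Most of this stands. It shows what was probably intended and that the confidence limits should stay. It does not say which of three defined baselines the code means, and it does not supply the missing conversion or the two-group CMH runs.

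A reader might infer that the planned power is lost, or that type I error is inflated. The documents support neither. Nothing in the SAP tells the analyst to compare a two-sided p-value with 0.025, and doing so would be conservative in the favourable direction. A reader might also infer that the single-baseline model would change the result; the SAP has no figures from which to show that.

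**Conclusion.** The mismatch between Appendix E and the text is real for both primary endpoints, and worth correcting before unblinding. The baseline covariate is a direct contradiction of unknown size. The sidedness and 2-df points are gaps in the code; the decision rule itself is clear.

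The stated power is unaffected. The conditional loss in step 4 (for one dose, about 5 points for s-BA 60% v 10%, 10 points for 50% v 10%, and 6 to 7 points for pruritus) arises only if an analyst sets aside the 1-sided rule. These figures assume 20 evaluable patients per arm, section 5's effect sizes, no stratification or covariates in the simulation, and the default two-sided output of the SAS statements shown.

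**What to change.** In Appendix E:

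- Change the right-hand side of the ANCOVA model line to `trt am_baseline pm_baseline pfic ageclass`.
- Show the CMH call three times, each with a two-level treatment variable: pooled odevixibat v placebo, 40 µg/kg/day v placebo, and 120 µg/kg/day v placebo.
- State for both endpoints that the 1-sided p-value is half the two-sided value when the estimate favours odevixibat (common odds ratio above 1, or LS mean difference above 0), and 1 minus half otherwise. State that these values enter the 0.025 comparison and the adjusted p-value.
- Keep the two-sided 95% confidence intervals as coded.

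The cost is a few lines of text and code. No endpoint, alpha level, sample size or stated power changes.
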